#### 2. STUDY OBJECTIVES AND ENDPOINTS

# 2.1. Study Objectives

## 2.1.1. Primary Objectives

The primary objectives for this study are:

- To confirm the safety and tolerability of magrolimab monotherapy in R/R AML and MDS and of magrolimab in combination with azacitidine in previously untreated patients with AML or MDS and patients with R/R AML and MDS
- To evaluate the safety, tolerability, and efficacy of magrolimab monotherapy in R/R AML/MDS, and of magrolimab in combination with azacitidine in previously untreated patients with AML/MDS or R/R AML/MDS as measured by complete remission (CR) rate for patients with AML and higher-risk MDS
- To evaluate the safety, tolerability, and efficacy of magrolimab monotherapy or in combination with azacitidine in low-risk MDS patients as measured by RBC transfusion independence rate

## 2.1.2. Secondary Objectives

The secondary objectives for this study are:

- To evaluate the PK profile of magrolimab alone and in combination with azacitidine
- To evaluate the immunogenicity of magrolimab
- To evaluate the efficacy of magrolimab alone or in combination with azacitidine as
  measured by duration of CR (DCR); objective response rate (ORR); CR with partial
  hematologic recovery; duration of response (DOR) for patients with AML; DCR for
  higher-risk MDS; ORR and DOR for patients with MDS; RBC transfusion
  independence; mean hemoglobin increase on treatment; progression-free survival
  (PFS); relapse-free survival (RFS), event-free survival (EFS); and OS
- To assess the level of MRD negativity

# 2.2. Study Endpoints

# 2.2.1. Primary Endpoints

The primary endpoints for this study are:

[figure not shown]
- Measurement of AEs according to National Cancer Institute Common Terminology
  Criteria for Adverse Events (NCI CTCAE) Version 4.03 or customized AE severity
  grading as defined in the protocol (Appendix A)
- CR rate for patients with AML as defined by the Investigator according to
  protocol-specified criteria (Appendix B), which are based on European Leukemia Net
  (ELN) AML recommendations (Döhner 2017), CR rate for patients with MDS as
  defined by the IWG 2006 MDS response criteria (Cheson 2006)

 8-week RBC transfusion independence rate for patients with low-risk MDS as defined by the lack of RBC transfusions for at least an 8-week consecutive period at any time after starting therapy

# 2.2.2. Secondary Endpoints

The secondary endpoints for this study are:

- Magrolimab concentration versus time measurements
- ADA to magrolimab
- Objective response in AML based on ELN AML recommendations (Döhner 2017)
  and IWG AML response criteria, or ORR (Cheson 2003) in MDS as defined by IWG
  2006 MDS response criteria (Cheson 2006); CRh; DCR and DOR for patients with
  AML; DCR and DOR for patients with MDS; RBC transfusion independence (no
  RBC transfusions for at least an 8-week consecutive period); 12-week RBC
  transfusion independence rates; mean hemoglobin increase on therapy; and, where
  appropriate, PFS, RFS, EFS, and OS for patients with AML or MDS
- Level of MRD negativity using a multiparameter flow cytometry-based assay for patients on therapy

#### 3. STUDY DESIGN

## 3.1. Overall Study Design

This trial is an open label, multicenter Phase 1b trial investigating the following:

- Magrolimab monotherapy or in combination with azacitidine in patients with relapsed and/or refractory AML or MDS (including R/R low-risk RBC transfusion-dependent MDS patients)
- Magrolimab in combination with azacitidine in newly diagnosed intermediate/high/very high-risk MDS patients
- Magrolimab in combination with azacitidine in newly diagnosed AML patients ineligible for standard induction chemotherapy (including TP53 mutant AML)
- Magrolimab monotherapy or in combination with azacitidine for RBC transfusion-dependent low-risk MDS patients

The study includes 4 groups of patients:

- R/R Cohorts: AML or MDS patients who have not previously received magrolimab, who will receive magrolimab monotherapy in the safety run-in cohort or magrolimab in combination with azacitidine in the expansion cohort on this study, as well as an R/R MDS Magrolimab Monotherapy Cohort that will enroll up to 23 R/R MDS patients.
- TN/U Cohorts: AML patients ineligible for standard induction chemotherapy and previously untreated intermediate/high/very high-risk MDS patients by IPSS-R, who will receive magrolimab in combination with azacitidine on this study, with at least 92 intermediate- to very high-risk MDS patients treated (with a combination of magrolimab 30 mg/kg weekly [n = 36] and 30 mg/kg Q2W [n = 56] dosing, plus azacitidine) and approximately 62 TP53 mutant TN/U AML patients (approximately 172).
- RBC Transfusion-dependent Low-risk MDS Cohort: RBC transfusion-dependent very low- to low-risk MDS patients who have failed or are intolerant to ESAs or lenalidomide (for del5q patients) who will receive magnolimab monotherapy or in combination with azacitidine on this study (approximately 20).

 Rollover Cohort: Patients who received magnolimab in the Phase 1 R/R AML study (SCI-CD47-002), who will continue magnolimab monotherapy on this study (total N = up to 8).

The R/R Cohorts consist of 2 cohorts: 1) an R/R Safety and Expansion Cohort, and 2) an R/R MDS Magrolimab Monotherapy Expansion Cohort. The R/R Safety and Expansion Cohort consists of an initial evaluation of magrolimab monotherapy in R/R MDS/AML patients, followed by an expansion cohort of magrolimab + azacitidine in R/R MDS/AML patients. As of Amendment 3, in the first stage, patients in the R/R Safety Cohort have been treated at the maintenance dose of 30 mg/kg twice weekly; going forward, these patients will be treated weekly at the maintenance dose of 30 mg/kg, as determined by the Clinical Trial Steering Committee (CTSC) based on clinical, PK, and PD data. This safety run-in will confirm the safety profile of magrolimab monotherapy at this dose level in an expanded R/R population. Approximately 30 days after enrollment is completed in the R/R Safety Cohort, the CTSC will assess the safety data to determine whether enrollment may begin in the TN/U Dose Evaluation Cohort. In addition, the CTSC will also determine whether enrollment will proceed to an initial 36-patient R/R Expansion Cohort, based on safety and efficacy data, which will be conducted with magrolimab in combination with azacitidine as per Amendment 5. Based on emerging data, the CTSC may decide to enroll additional patients beyond 36 for further safety, efficacy, or dosing information.

The R/R MDS Magrolimab Monotherapy Cohort was added in Amendment 6. Per FDA feedback, a magrolimab monotherapy cohort in R/R MDS will be evaluated to further define the activity of magrolimab to the contribution of magrolimab + azacitidine in MDS to support a potential single-arm approval of magrolimab + azacitidine in MDS. Patients will be enrolled in a Simon's 2-stage design to evaluate for potential futility. Patients who do not achieve an objective response with magrolimab monotherapy at the protocol-defined first response assessment may have azacitidine added by discretion of the Principal Investigator with Sponsor approval, according to the schedule of azacitidine outlined in the R/R cohorts.

The TN/U Cohort will be enrolled in 2 stages. In the first stage, the study will investigate the safety and tolerability of magrolimab and azacitidine in a 3+3 dose evaluation design, in previously untreated AML patients who are unfit for standard combination chemotherapy and previously untreated intermediate/high/very high-risk MDS patients. The same dose level of magrolimab used in the R/R Safety Cohort will be initially evaluated in combination with the standard dose of azacitidine in the TN/U Dose Evaluation Cohort. Optional additional dose cohorts may explore higher or lower doses in increments of up to 50% of the maximum prior dose, as determined by the CTSC based on emerging PK, pharmacodynamic, and clinical data. A total of up to 18 patients may be treated in the TN/U Dose Evaluation Cohort. In the second stage, a recommended dose and schedule will be selected by the CTSC for treatment of up to 30 patients in the TN/U Expansion Cohort, which will be evaluated for efficacy of magrolimab in combination with azacitidine. The same dose level of magrolimab used in the R/R Safety Cohort will be initially evaluated in combination with the standard dose of azacitidine in the TN/U Dose Expansion Cohort. Per CTSC and Amendment 6, the magrolimab dosing was changed to 1 mg/kg on Days 1 and 4; 15 mg/kg on Day 8; 30 mg/kg on Days 11, 15, and 22; 30 mg/kg weekly for Cycle 2; and 30 mg/kg Q2W starting Cycle 3 and thereafter. In addition, based on Amendments 5 and 6, the TN/U Expansion Cohort was expanded to a total of 122 patients, which will include at least 92 patients with MDS and an additional 12 slots for TP53 AML per CTSC decision September 2019. For a higher-risk, untreated, MDS-only expansion, an evaluation will occur after 36 patients have undergone the first response assessment. If the CR rate for magrolimab+azacitidine is at least 35.5%, then subsequent enrollment can continue. After this initial efficacy evaluation (as a part of Amendment 6), at least 56 additional patients will be enrolled at a magrolimab 30 mg/kg Q2W dosing regimen in the higher-risk untreated MDS expansion. Enrollment does not need to be paused during the 36-patient evaluation prior to the additional 56-patient expansion. As part of Amendment 6, a subcohort of approximately 32 TN/U AML (12 patients plus an additional 20) patients with a TP53 gene mutation was added. This addition is based on initial encouraging efficacy data observed in the TN/U Cohort in patients with a TP53 gene mutation. Based on emerging data, the CTSC may decide to enroll additional

patients beyond the 20 patients for further safety, efficacy, and/or dosing data. Per CTSC decision in July 2020 and captured in Amendment 7, an additional 30 TP53 mutant AML patients were added to the TN/U Expansion Cohort (n = 62).

The RBC Transfusion-dependent Low-risk MDS cohort will consist of approximately 20 patients and be based on a Q4W magrolimab dosing schedule administered starting Cycle 2. Given that a higher dose of magrolimab (60 mg/kg) will be tested in this cohort, the first 6 patients will be treated in a safety run-in cohort. These 6 patients will be treated with magrolimab monotherapy for the first 2 cycles, followed by a response assessment. Patients who do not respond to magrolimab monotherapy by this time may have azacitidine added to their treatment regimen. Based on the initial safety and efficacy data for these 6 patients, the CTSC will determine whether the remaining 14 patients will be treated as magrolimab monotherapy or in combination with azacitidine, as well as the dose of magrolimab. After a safety evaluation of these 6 patients by the CTSC, the remaining 14 patients can be simultaneously enrolled. Based on emerging data, the CTSC may decide to enroll additional patients for further safety, efficacy, or dosing information. These additional patients may be treated with either magrolimab monotherapy or magrolimab in combination with azacitidine. Patients may have their magrolimab dose interval changed (i.e., to more frequent [Q2W] or less frequent [> Q4W]) at any time on therapy based on CTSC recommendations or Sponsor requirement.

The Rollover Cohort will be open to all patients (maximum of 8) on the existing Phase 1 AML trial (study SCI-CD47-002) who are deriving ongoing clinical benefit from magrolimab therapy. Patients in the Rollover Cohort may receive the same dose level and schedule (i.e., twice weekly) of magrolimab monotherapy as previously received on the Phase 1 AML study (SCI-CD47-002), or may transition to once-weekly dosing in this study at the discretion of the Investigator and with Sponsor approval. At the discretion of the CTSC for this study, Rollover patients who are receiving lower doses may be escalated to a higher dose deemed to be safe by the CTSC for this study.

Patient participation will include screening, treatment, and follow-up. Screening will last up to 30 days before first dose of study treatment (magrolimab and/or azacitidine), during which time the patient's eligibility and baseline characteristics will be determined. Study treatment may be continued until an unacceptable drug-related toxicity occurs or until disease progression or loss of clinical benefit. Post treatment, patients will be observed for disease progression and survival until death, withdrawal of consent, or the end of the study, whichever occurs first. For patients who come off study treatment to receive a bone marrow transplant, follow-up for disease progression and collection of SOC bone marrow biopsy/aspirate results will continue until documented disease progression occurs.

The end of the entire study for all patients is defined as the date on which the last patient completes the last study visit (follow-up for safety, disease progression or survival), or when the CTSC or Sponsor decides to end the study.

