## **Sample Size Justification**

A total of approximately 287 efficacy evaluable patients may be enrolled.

For the R/R Safety Cohort and Expansion Cohort, approximately 46 patients may be enrolled, including 10 patients treated in the safety run-in cohort and 36 patients treated in the expansion cohort. For the R/R Safety Cohort, 10 patients were enrolled, and this cohort was closed to further enrollment as of Amendment 3. Based on safety and efficacy data, the CTSC may decide to expand the R/R Expansion Cohort to include additional patients. An ORR of 17% has been reported in patients with R/R AML who have been treated with azacitidine (Itzykson 2015). For an estimated response rate of 33% or higher, 36 patients would provide a 95% confidence interval, with the lower bound to exclude 18.6%, the azacitidine monotherapy efficacy rate.

For the TN/U Dose Evaluation Cohort, up to 18 patients can be enrolled based on a 3+3 dose de-escalation design assuming 3 potential dose cohorts with a maximum of 6 patients treated per cohort. For the TN/U Dose Evaluation Cohort, 8 patients were enrolled, and this cohort was closed to further enrollment as of Amendment 5. For the TN/U Expansion Cohort, an initial sample size of 30 patients was proposed so that the 95% confidence interval of the desired 35% or higher CR rate would exclude a known CR rate of 17.85% for azacitidine alone. This sample size calculation was based on inclusion of both TN/U AML and higher-risk MDS patients. For the higher-risk, untreated, MDS-only Expansion Cohort added in Amendment 5 (16 originally enrolled MDS patients + 76 additional patients for n = 92), an evaluation will occur after 36 patients have reached the first response assessment (Cycle 3 Day 1); however, enrollment will continue and will not be paused in the interim. A sample size of 36 patients provides 80% power to reject the null hypothesis that the CR rate is 16.5% or lower at 2-sided 0.05 significant level, assuming the true magrolimab+azacitidine CR rate is at least 35.5% (19%

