As of May 2019 in Study 5F9005, clinical activity was assessed for magrolimab monotherapy in R/R AML/MDS and for magrolimab in combination with azacitidine in TN/U AML/MDS (Sallman 2019). Magrolimab monotherapy induced an objective response in 1 of 10 (10%) R/R AML/MDS patients (with 1 AML patient achieving morphologic leukemia-free state [MLFS]). With magrolimab in combination with azacitidine, 11 of 11 (100%) MDS patients achieved an objective response, with a CR+partial remission (PR) rate of 55%. In untreated AML patients, magrolimab in combination with azacitidine induced an objective response in 9 of 14 (64%) of patients, with 36% achieving a CR and 14% achieving a CR with incomplete blood count recovery (CRi). Median time to response at 1.9 months for the combination treatment was more rapid than that expected for azacitidine alone (4 to 6 months). In MDS patients, 3 of 7 (43%) responding patients with abnormal cytogenetics at baseline

achieved a complete cytogenetic response, with 2 of 10 responders with minimal residual disease (MRD) assessment achieving MRD negativity by flow cytometry. In summary, in a limited sample size, magrolimab in combination with azacitidine has meaningful clinical activity that appears to be enhanced compared to azacitidine monotherapy. Further results are found in the IB.

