# 3.3.6. TN/U Expansion Cohort

Patients in the Expansion stage of the TN/U Expansion Cohort will receive the RP2DS determined in the TN/U Dose Evaluation Cohort. For the TN/U Expansion stage, patients may be enrolled simultaneously without an observation time between patients. The CTSC may alter the dosing scheme including, but not limited to, exploring a dose schedule of weekly or up to Q4W, if supported by emerging PK and clinical safety and efficacy data. Based on emerging clinical data, including efficacy data, the TN/U Expansion Cohort may be increased beyond 30 patients as determined by the CTSC.

Based on a Type B End of Phase 1 meeting with the FDA in May 2019, the TN/U Expansion Cohort was expanded in Amendment 5 to include untreated intermediate to very high-risk MDS patients, as assessed by IPSS-R, to include at least 91 patients as a single-arm trial for a potential BLA in higher-risk untreated MDS. These 91 patients are inclusive of MDS patients already treated in the TN/U Dose Evaluation and Expansion Cohorts. In a Type A meeting with the FDA in November 2019, it was agreed that the primary endpoint for potential approval can be CR rate with duration of CR.

An efficacy evaluation will be made after 36 evaluable MDS patients have undergone the first response assessment. If the CR rate for magrolimab and azacitidine is at least 35.5%, then an additional 56 patients will be treated in expansion at a magrolimab dosing regimen of Q2W. Enrollment does not need to be paused during the 36-patient evaluation prior to the additional 56-patient expansion. The 56-patient expansion would bring the total number of MDS patients in the TN/U Expansion Cohort to n = 92. The overall MDS expansion to 92 patients will be considered the MDS Registrational Cohort.

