assessment (Cycle 3 Day 1); however, enrollment will continue and not be paused in the interim. A sample size of 36 patients provides 80% power to reject the null hypothesis that the CR rate is 16.5% or lower at 2-sided 0.05 significant level, assuming the true magrolimab + azacitidine CR rate is at least 35.5% (19% improvement). The null CR rate of 16.5% is based on the pivotal randomized trial leading to azacitidine approval in MDS reanalyzed by IWG 2000 criteria (Silverman 2006), where the upper bound of the 1-sided 95% confidence interval for azacitidine CR rate is 16.5%, with a point estimate of 10%. Based on Amendment 6 and FDA feedback for a single-arm trial to support a potential BLA, the sample size of the TN/U MDS-only Expansion Cohort for untreated, higher-risk MDS patients was further increased to include a cohort of 56 patients with MDS at a magrolimab Q2W dosing regimen. A sample size of 56 patients provides 80% power to reject the null hypothesis that the CR rate is 16.5% at a 2-sided 0.05 significant level, assuming the true magrolimab+azacitidine CR rate is at least 31.5%. The null CR rate of 16.5% is based on the same assumption for azacitidine monotherapy as above. A combined planned sample size of 92 patients for the MDS Registrational Cohort will provide an 80% power to reject the updated null CR rate of 23.5% at a 2-sided 0.05 significant level, assuming the true magrolimab+azacitidine CR rate is 36.5%.

Per the CTSC decision in September 2019 and Amendment 6, a subcohort of TP53 mutant TN/U AML patients was added. Initially, 12 patients and then an additional 20 patients will be enrolled. Analysis of these patients will include all TP53 mutant patients meeting subcohort eligibility enrolled prior to the Amendment/CTSC decision. A sample size of 32 patients was selected to evaluate the initial efficacy of magrolimab+azacitidine as compared to available therapies (most notably venetoclax+hypomethylating agents) in TP53 mutant AML. While venetoclax in combination with hypomethylating agents (azacitidine or decitabine) is approved in newly diagnosed AML patients who are ineligible for intensive chemotherapy, their efficacy in TP53 mutant AML patients is limited. Per a recent report, the CR+CRi rate of venetoclax+hypomethylating agent in TP53 mutant AML was 47%, with a median duration of CR of 5.6 months and a median overall survival of 7.2 months (DiNardo 2019). In contrast, in all-comer AML patients, the CR+CRi rate was 67% with

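### The 36-patient rule for the MDS expansion uses the design alternative (35.5%) as the observed cut-off, so a drug as good as planned misses it about 47% of the time; other sections describe the same look with no condition

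*Protocol*

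**What the plan says.** Two design sections attach a numerical condition to the 36-patient look. Section 3.1: "If the CR rate for magrolimab+azacitidine is at least 35.5%, then subsequent enrollment can continue". Section 3.3.6: "If the CR rate for magrolimab and azacitidine is at least 35.5%, then an additional 56 patients will be treated in expansion". Both add that enrolment need not pause while the evaluation is made.

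The same 35.5% appears in Section 11.4 and the Synopsis as a planning assumption: "A sample size of 36 patients provides 80% power to reject the null hypothesis that the CR rate is 16.5% or lower", "assuming the true magrolimab + azacitidine CR rate is at least 35.5"%, at a 2-sided 0.05 level.

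The timing is given in the Synopsis, Sample Size Justification: "an evaluation will occur after 36 patients have reached the first response assessment (Cycle 3 Day 1"), which Section 7.3.8 places about 8 weeks after the start of treatment.

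Elsewhere the look carries no condition. The Synopsis, Overall Study Design, says that enrolment goes on during the evaluation and that at least 56 more patients will be enrolled. The Synopsis, Sample Size Justification, gives no threshold and says "however, enrollment will continue and will not be paused in the interim". Section 11.4 says the same in almost the same terms.

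**The concern.** A true rate assumed for power and an observed rate required for a decision are different things. If the observed result must reach the rate for which the study was powered, a drug that performs exactly to plan clears the bar only slightly more than half the time. The 80% power stated for 36 patients and the go criterion therefore describe two different decisions.

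It matters because the 36 and the 56 together form the 92-patient MDS Registrational Cohort, intended to support a potential licence application and carrying the formal test against a CR rate of 23.5% (Section 11.8.1.1). A reader of Sections 3.1 and 3.3.6 would conclude that the second stage depended on an efficacy criterion. A reader of the Synopsis and Section 11.4 would conclude that it did not. A regulator could fairly ask which was applied and whether 35.5% was reached.

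**Working it through.** **Inputs.** n = 36, null 16.5%, alternative 35.5%, 2-sided 0.05, power 80% (Section 11.4). Observed threshold 35.5% (Sections 3.1 and 3.3.6). Alternative of 31.5% for the 56 Q2W patients, and null 23.5% with alternative 36.5% for the pooled 92 (Synopsis, Sample Size Justification; Section 11.4).

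**Reproducing the stated 80%.** Normal approximation, null variance under the null and alternative variance under the alternative:

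- Null SE = √(0.165 × 0.835 / 36) = 0.0619
- Alternative SE = √(0.355 × 0.645 / 36) = 0.0798
- Power = Φ[(0.355 − 0.165 − 1.96 × 0.0619) / 0.0798] = Φ(0.862) = 80.6%

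The required n is 35.4, rounded up to 36. The stated power is reproduced.

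**Translating the go criterion.** 0.355 × 36 = 12.78, so 13 CRs are needed (36.1%); 12/36 = 33.3% fails.

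**Cut-offs that match the stated test.** With z = (x/36 − 0.165) / 0.0619, x = 10 gives 1.82 and x = 11 gives 2.27, so the chi-square test rejects from 11/36. An exact binomial test with upper tail at most 0.025 rejects from 12/36 (tail 0.0103; at 11 it is 0.0266).

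| Rule | P(reached), true 16.5% | P(reached), true 35.5% |
|---|---|---|
| ≥ 11/36 (chi-square) | 2.7% | 78.4% |
| ≥ 12/36 (exact) | 1.0% | 66.7% |
| ≥ 13/36 (go criterion) | 0.36% | 53.2% |

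**Probability of missing the go criterion**, 1 − P(X ≥ 13) with X binomial(36, p):

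- p = 31.5%: 66.8%
- p = 35.5%: 46.8%
- p = 36.5%: 41.8%

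A true rate of about 41.7% is needed for an 80% chance of passing.

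**If the criterion was binding.** For the pooled 92 at a true 36.5%, the chi-square test of 23.5% rejects from 30/92 (power 81.1%, in line with the stated 80%) and the exact test from 31/92 (74.6%). The probability of passing the gate and then rejecting is

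Σ over x ≥ 13 of P(X₁ = x; 36, 0.365) × P(X₂ ≥ r − x; 56, 0.365),

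which is 54.4% for r = 30 and 52.1% for r = 31. This counts every eventual CR among the 36 as present at the look. Later CRs can only lower the chance of passing, so both figures are upper limits.

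**The case against.** **The clause may not be a stopping rule.** Section 3.1 says enrolment can continue, gives no action on a miss, goes on to say that 56 more patients will be enrolled, and waives any pause. The monotherapy cohort's two-stage rule, by contrast, says outright that the cohort will be stopped. This is a fair reading. It does not remove the condition, which Section 3.3.6 states plainly; it is a reason to say in the text which reading holds.

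**A demanding bar can be a sponsor's choice.** True, and against the exact test the criterion is only one patient stricter. But nothing presents it as a deliberate choice, and the number coincides with the planning alternative.

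**The stated power is not wrong.** This stands. The 80% for 36 and the 80% for 92 are both reproduced, and the protocol does not claim that the latter allows for a go decision.

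Three stronger inferences are tempting and not supported:

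- *That only about half of CRs are visible at week 8.* Section 1.2.2.3 reports "Median time to response at 1.9 months for the combination treatment", but that is time to any response, not to CR, and covers AML and MDS. Response is recorded at visits, so a median near the first visit is compatible with well over half of responders being recorded there. Week 8 is also a minimum: patients enrolled earlier may have had later assessments. CRs first reached after the look would raise the failure rate, but the protocol gives no share, so no figure is claimed.
- *That enrolment continued whatever the result.* The Synopsis sample-size text and Section 11.4 speak of the interim only. Only the Synopsis design text is plainly unconditional.
- *That the cohort was expanded although the criterion was missed.* The protocol does not report the 36-patient CR rate; the criterion may have been met.

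**Conclusion.** The point holds as an ill-set and inconsistently stated decision rule. At the planned 35.5% the criterion is missed 46.8% of the time, against 21.6% for the chi-square cut-off of the stated test and 33.3% for the exact one. These figures rest on binomial sampling with every eventual CR counted at the look, so for a given true rate they understate the failure probability if some CRs come later. The contradiction between Sections 3.1 and 3.3.6 on one side and the Synopsis design text on the other is real, and the consequence of a miss is nowhere defined. The joint figures of about 54% and 52% apply only if the rule was binding. The cohort is marked closed to enrolment (Table 7-2), so what is at stake now is how the evaluation is described and reported.

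**What to change.** Reconcile Sections 3.1 and 3.3.6 with the Synopsis and Section 11.4. State, according to how the CTSC actually applied it, whether the 36-patient look was a binding gate or a non-binding evaluation. Keep the 35.5% criterion on record rather than deleting it after the cohort has closed, and report the observed 36-patient CR rate against it in the clinical study report.

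If the look was binding, add to Section 11.4 that the 80% power for 92 patients takes no account of the gate, and that the probability of passing it and then rejecting 23.5% at a true 36.5% is at most about 54% (chi-square) or 52% (exact), with all CRs assumed present at the look.

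The cost is wording only, plus a less favourable figure on the page if the gate was binding. Sample size, data collection and the primary test are unchanged.
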